Engaging Working Memory and Distress Tolerance to Aid Smoking Cessation
NCT03565497
R21 DA046963

Updated: 8/5/2019

PROTOCOL

Design Overview

This study is designed to evaluate the success of mechanistic target engagement in two specific contexts: under standard smoking conditions and under nicotine deprivation (stress) conditions. After screening, consent, and baseline assessment, participants selected on the basis of inclusion/exclusion criteria will be randomized to one of three intervention conditions: (1) a health-education control condition (CC), (2) a mindfulness training condition (MT), or (3) a mindfulness training condition combined with training applying mindfulness skills in the context of interoceptive exposure (Mindfulness+IE). Following 6 sessions of these interventions, delivered over 3 weeks, participants will then undergo the standard smoking assessment of mechanistic targets. Two days later (and matching the progression to quit-attempt challenges following treatment), participants will undergo the deprivation window assessment (14 hours of smoking abstinence) of these same mechanistic targets, followed by evaluation of lapse behavior and smoking topography in the McKee paradigm to yield: (1) latency to initiate smoking during a monetarily reinforced delay period, (2) the number of cigarettes smoked during a subsequent 60-minute self-administration period, and (3) exploratory analysis of smoking topography: puff volume, puff duration, and inter-puff interval. Participants will be recruited to Boston University through study advertisements targeted to low SES neighborhoods, with attention to health service centers and religious institutions serving low SES individuals. Investigators will work closely together to ensure the scientific integrity (rigor and reproducibility) of the project and data analyses.

Participant Selection

We anticipate consenting and randomizing up to 107 participants in order to reach an assessed sample (defined as providing post-treatment assessments, including the McKee protocol) of 75, low SES, male and female smokers (ages 18-65). For inclusion in the study, participants must (1) be between 18 and 65 years of age; (2) have reported household income of less than \$30,000 per year; (3) be a regular smoker for at least one year; (4) report daily smoking (minimum of 5 cigarettes per day and biochemically confirmed via Carbon Monoxide [CO] analysis; > .10 ppm CO); and (5) and not be presently engaged in a quit attempt. Exclusion criteria include history of psychosis as determined by a brief psychotic screen, pregnancy, nursing mothers, medical conditions that would contraindicate smoking (e.g., current diagnoses of chronic medical diseases including heart disease, chronic obstructive pulmonary disease, or seizure disorders - assessed during telephone prescreen and initial assessment via medical checklist), nicotine use other than cigarette smoking, current use of any pharmacotherapy for smoking cessation, or insufficient command of the English language (i.e., cannot carry on a conversation with an interviewer in the English language or read associated text).

Feasibility and Participant Compensation

The study team and consultants have a rich publication history reflecting collaboration on studies of health behaviors, distress intolerance, and, specifically smoking characteristics and treatment outcome.^{1,73,76,90-93} [name] at Boston University has a history of successfully attracting smokers for psychopathology studies, easily completing 100 screens per year. Moreover, [name] is directing mindfulness interventions to low SES adolescents recruited to his ongoing study, R21DA041531. Recruitment/adherence is aided in the current study by financial compensation for all assessments and intervention sessions, with compensation of up to \$180 per participant, depending on McKee Lapse paradigm results.

Procedures and the McKee Protocol

Following telephone screening for basic eligibility, participants will be scheduled for an informed consent interview and subsequent baseline assessment session. Interventions are to be completed over the subsequent 3 weeks, and post-treatment assessments of the mechanistic targets are scheduled for one-week (standard smoking assessment) and one week + 2 days (deprivation-window assessment) from the last intervention session. For the standard smoking window assessments, participants are asked to smoke .5 hour before the scheduled assessment session. The deprivation-window assessment is scheduled two days later, (for example, scheduled for 12:00 noon, with smoking to cease at 10PM the night before). Upon arrival to the lab, nicotine abstinence will be verified by expired CO levels, as determined by a cut-off of half of the participant's screening session CO concentration or <10 PPM (those failing will be rescheduled). After verification of abstinence, participants will complete assessment of the triple-risk mechanistic target variables. These assessments will be followed by the McKee Lapse protocol ([name], *Study Consultant*, will train the study team and help monitor quality in these procedures): participants will be instructed that over the next 50 min, they will have the option to initiate a cigarette self-administration (smoking) session at any point or to delay initiation in exchange for monetary reinforcement. If participants choose to delay, they will be awarded funds for each 5-minute increment they are able to resist smoking. Once participants choose to end the delay period in order to smoke (or resist smoking for the entire 50 minute delay period), they will then participate in a 60-minute cigarette self-administration session, in which they will be given the choice to either smoke their

preferred brand of cigarettes or receive monetary reinforcement for cigarettes not smoked. Participants will be given funds at the beginning of the self-administration session and will lose a portion of the funds for each cigarette smoked. When participants smoke in this protocol, we will use the Clinical Research Support System (CReSS; Plowshare Technologies, Borgwaldt KC, Inc) to measure smoking topography. The reliability and acceptability of use of the portable CReSS device is well documented,^{88,94} and is recommended over direct observation. Topography data will include puff CO volume, puff duration, and inter-puff interval. Puff level data will be averaged to compute mean topography variables for each participant.

Baseline Assessments

- **Demographics.** Participants will be asked to provide standard demographic information (age, gender, race/ethnicity) as well as history of medical problems and current treatments.
- **Smoking History Questionnaire.** Smoking history and pattern will be assessed with a semi-structured interview with items targeting smoking frequency, age of smoking initiation, years of being a regular smoker, etc. The Timeline follow-back method will be used to establish degree of cigarette use in the last 30 days (a baseline predictor).
- **Fagerström Test for Cigarette Dependence (FTCD).** The FTCD is a six-item scale designed to assess gradations in cigarette dependence.⁹⁵ The FTCD will be used as a baseline covariate in the analyses.
- **Questionnaire of Smoking Urges-Brief (QSU-Brief).** The QSU-Brief measures urge to smoke and craving.^{96,97} The baseline and deprivation window Total Craving Scores will be used as predictors.
- **Executive Function – Behavioral Regulation.** Baseline levels of behavioral regulation will be assessed with the Behavioral Regulation Index from the from the SOBC assay, Behavioral Rating Inventory of Executive Function – Adults (BRIEF-A, <http://scienceofbehaviorchange.org/measures/>).
- **Psychological Distress.** Baseline levels of psychological distress will be assessed with the SOBC assay, Kessler Psychological Distress Scale (K6+, <http://scienceofbehaviorchange.org/measures/>).

Mechanistic Targets: The Triple-Risk Variables

Each of the mechanistic targets will be assessed at the post-intervention standard-smoking and deprivation-window assessments.

- **Negative Affectivity/Stress:** Negative affect will be assessed with the SOBC assay, PANAS (PANAS-state negative (<http://scienceofbehaviorchange.org/measures/>), and withdrawal symptoms will be assessed with the Wisconsin Smoking Withdrawal Scale (WSWS).⁹⁸ Each of these mechanistic targets will be assessed at the standard smoking and deprivation-window assessments.
- **WM.** We focus on WM capacity as a mechanistic target due to its centrality to executive functions; its predictive validity across a wide range of health behavior applications, specifically including smoking; relevance as a modifiable treatment target; and interaction with negative affectivity/stress.¹ To provide multi-domain assessment of WM,^{99,100} we will adopt 3 specific SOBC assays : Adaptive N-Back, Digit Span, and Spatial Span (<http://scienceofbehaviorchange.org/measures/>). [name], *Study Consultant*, will aid the study team in quality control for these assessments.
- **Distress Tolerance.** We likewise focus on DT as a mechanistic target due to its predictive validity across a wide range of health behaviors (specifically including smoking); relevance as a modifiable treatment target; and amplification of negative affectivity/stress.¹ Because self-report and behavioral measures of DT are only partially correlated,³⁵ we will utilize both assessment strategies. For self-report we will use the ASI-3, an 18-item measure of AS.¹⁰¹ The ASI-3 has sound psychometric properties, including excellent internal consistency, predictive validity, and reliability among treatment-seeking smokers.¹⁰² Behavioral Distress Tolerance will be assessed with the computerized Mirror-Tracing Persistence Task (MTPT-C),¹⁰³ with evidence this measure captures the inability to tolerate distress and not just the experience of distress itself.¹⁰⁴ [name] and [name] will aid the study team in quality control for these assessments.

Interventions

All interventions are delivered in six, 90-minute individual sessions over 3 weeks. Sessions will be recorded for supervision/quality assurance review by [name].

- **CC:** The wellness education control condition (CC) will be modeled after that used in our studies of exercise for smoking cessation,⁷³ but delivered in an individual format. Content focuses on discussions of a variety of healthy lifestyle topics, such as healthy eating, time management, recommended health screenings, and cancer and cardiovascular prevention. Content is delivered using a combination of lectures, videos, handouts, and discussions while allowing participants to set their own realistic wellness goals, which they can gradually incorporate into their lives. [name], *Study Consultant*, will aid the study team in quality control of this intervention.

- **MT:** Mindfulness training will be adapted for 6 individual sessions from previous MT manuals for substance dependence.¹⁰⁵⁻¹⁰⁷ The length of treatment in the current protocol corresponds well to the mean number of sessions [5.2] attended by smokers in treatment, even when eight sessions are offered.¹⁰⁵ Formal intervention elements include: (1) a body scan designed to teach participants to pay attention to specific parts of their bodies as a strategy to increase attentional capacities/reduce habitual mind-wandering; (2) non-judgmental awareness, and (3) 'awareness of breath' meditation, with an additional focus on helping participants become more aware of the present moment and refrain from habitually engaging in self-related pre-occupations concerning the future or the past. Informal daily practices include (1) performing daily activities mindfully, (2) setting daily aspirations, and (3) techniques designed for cravings (recognize/accept/investigate mind-states, emotions, and body sensations from moment-to-moment). Participants will be asked to record both the number of minutes and number of episodes of mindfulness practice each day using structured diaries. [name], *Study Consultant*, will aid the study team in adapting mindfulness skill training to the current protocol, and consult with [name] on treatment fidelity issues.
- **MT+IE.** This condition will mirror the MT condition for the first 4 individual sessions, then for the final 2 individual sessions, MT will be rehearsed under conditions of sensations of anxiety/tension induced by interoceptive exposure procedures (IE). [name] and the study team are adept in delivering IE training to those about to undergo benzodiazepine withdrawal sensations,⁶⁹⁻⁷¹ and to smokers as part of quit attempts.^{74,75} In the two in-session rehearsals (sessions 5 & 6 of mindfulness training), the focus will be on maintaining mindful, non-judgmental awareness despite the presence of induced bodily sensations of anxiety/tension.

Engaging Working Memory and Distress Tolerance to Aid Smoking Cessation

NCT03565497

R21 DA046963

Updated: 8/5/2019

Analytic Plan

Note: Due to limited sample size the full analytic plan for this project could not be enacted validly.

Analyses for outliers, non-normal distributions, nonlinear relations, and influence statistics will be conducted; data transformations will be considered where appropriate. We will analyze data using mixed effects regression models (MRM) because they allow inclusion of all participants regardless of missing data (which improves power and generalizability) and are the recommended method for longitudinal data analysis (Hamer & Simpson, 2009). For each analysis, the distribution of the DVs will be evaluated and appropriate linking functions and outcome distributions will be used if the DVs are not normally distributed (in these cases the analysis will be generalized linear mixed models). For all analyses, the following baseline assessments will be included as covariates in the analyses: cigarette use in the last 30 days, FTCD score, QSU score, BRIEF-A scores for the Behavioral Regulation Index, and psychological distress from the K6+ symptoms.

Aim 1. We will perform repeated-measures MANCOVAs using MRMs. IVs will be intervention condition (3 levels) and assessment context (smoking vs. deprivation; 2 levels). One MANCOVA will be performed for each of the three risk categories (stress reactivity, WMC, DT) with the multiple measures of each risk factor being the multivariate DVs. For Aim 1a, we will use contrasts to test whether Mindfulness and Mindfulness+IE will each significantly improve stress reactivity, WMC, and DT relative to the control condition (CC), during the standard smoking assessment. For Aim 1b, we hypothesize that Mindfulness+IE will significantly improve stress reactivity, WMC, and DT relative to both the Mindfulness and CC conditions, during the smoking deprivation assessment.

Aim 2: For Aim 2, we will examine the bivariate associations between the triple risk variables and McLee Lapse outcomes. We will attempt to balance the need to determine which individual variables at which assessment context are related to which outcomes, with the need to minimize the number of tests. Thus, multivariate MRM (MMRM) will be used with the 2 McLee Lapse outcomes as the multiple DVs. One MMRM will be performed for each individual risk variable, with the IVs in each MMRM being the 2 assessments (smoking context and deprivation context) of the individual risk variable. This MMRM will be compared to the same MMRM that constrains the coefficients of each IV to be equal. If the likelihood ratio test indicates that the constrained model does not fit the data worse than the unconstrained model, then the relation between the risk factor and the outcomes does not differ by assessment context. If the test is significant, assessment context would be considered a moderator of the relation between the risk factor and outcome. Further, we will include a dummy variable to differentiate the 2 outcomes (0=latency, 1=number of offers of cigarettes resisted). If an interaction between that dummy variable and an IV regression coefficient is significant, the relation between the risk factor and outcome is different for the 2 outcomes.

Aim 3: To determine which of the individual risk assays are related to outcomes over and above the other factors, including consideration of the assessment context of each risk factor, we will perform analyses similar to the MMRM in Aim 2 with the following differences: 1) if Aim 2 shows that the relation between a risk assay and outcomes did not differ by context, the 2 measures of the risk factor will be averaged across the 2 contexts and used as a single predictor, and 2) all the risk factors will be entered as simultaneous predictors of outcomes. Non-significant predictors will be dropped and the analysis rerun.

Exploratory Analyses: 1) In consideration of sex as a biological variable, sex and the interactions between sex and all predictors will be considered in exploratory analyses for each Aim. 2) We will examine whether ASI moderates the effects of treatment condition and context (stress) on the risk categories in Aim 1, by adding ASI and its interaction with the treatment condition and context to the MMRMs in Aim 1. 3) We will examine smoking topography as a predictor of outcomes in Aims 2 and 3. 4) We will examine number of intervention sessions attended and dropouts to aid data interpretation and future study planning.

Power Analysis. We used PinT 2.12 (Power in Two-Level models) to calculate the smallest effect size detectable given our N=75 at the deprivation assessment. Since no power analysis programs are available for multivariate MRM, we performed power analyses for the univariate MRMs knowing that power for the multivariate MRMs will be greater.¹⁰⁸ PinT indicated that we had greater than .80 power to detect an effect size of $d = .40$ for **Aim 1**, $d = .39$ for **Aim 2**, and $d = .48$ for **Aim 3**. As per research detailed above,^{54,63,64,71,82,109} there is preliminary evidence indicating that our interventions have the ability to activate mechanistic targets, and for mechanistic targets to be related to clinical outcomes, at effect sizes beyond these powered values.

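### The exploratory ASI moderation gives no time point, and the only ASI described is a post-treatment Aim 1 outcome, so its interaction cannot show who benefits

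*SAP*

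**What the plan says.** **Timing of the Aim 1 outcomes.** Under Mechanistic Targets, the protocol states: "Each of the mechanistic targets will be assessed at the post-intervention standard-smoking and deprivation-window assessments". Under Procedures and the McKee Protocol, these assessments "are scheduled for one-week (standard smoking assessment) and one week + 2 days (deprivation-window assessment) from the last intervention session". The targets are PANAS negative affect, WSWS, three working-memory tasks, ASI-3 and the mirror-tracing task (MTPT-C). ASI-3 is the self-report measure of distress tolerance (DT).

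**Baseline.** The protocol's Baseline Assessments list has demographics, smoking history, FTCD, QSU-Brief, BRIEF-A and K6+. None of the seven targets is on it. In the SAP, "the following baseline assessments will be included as covariates in the analyses: cigarette use in the last 30 days, FTCD score, QSU score", followed by BRIEF-A and K6+; no target is among these five either.

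**Aim 1 model.** "IVs will be intervention condition (3 levels) and assessment context (smoking vs. deprivation; 2 levels"; both levels are post-treatment. There is one multivariate model per risk category, "with the multiple measures of each risk factor being the multivariate DVs", so ASI-3 is a dependent variable of the DT model.

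**ASI as moderator.** SAP, Exploratory Analyses, item 2 enters ASI and its interactions with condition and context in the Aim 1 models. It names no visit. Item 4 of the same list plans a look at session attendance and dropouts.

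**Missing data.** The SAP prefers mixed models "because they allow inclusion of all participants regardless of missing data (which improves power and generalizability". The protocol anticipates "randomizing up to 107 participants in order to reach an assessed sample" of 75, and the SAP's power analysis uses 75 at the deprivation assessment. A note at the head of the SAP reads: "Due to limited sample size the full analytic plan for this project could not be enacted validly".

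**The concern.** A moderator analysis asks whether people who differ before treatment respond differently to it. That needs a value fixed before randomisation. The only ASI in the documents is measured after treatment, and the plan itself hypothesises that treatment will change it. Its interaction with condition then mixes three things: any true moderation, the treatment's effect on ASI-3, and noise between baseline and post-treatment scores. In the DT model the difficulty is sharper, since ASI-3 would help to predict itself.

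At stake is a conclusion about which smokers gain from mindfulness or from adding interoceptive exposure, which could be carried into the design of a later trial.

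Two smaller matters follow from the same schedule. Without a baseline value of each target, some precision and some protection against informative loss are given up. And the stated reason for using mixed models promises more than the schedule can deliver.

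**Working it through.** **1. The plan's own figures.** 75/107 = 70.1%, so 107 - 75 = 32, or 29.9%, are not fully assessed if both planning numbers are met. Because 75 counts people at the deprivation visit, anyone who attended only the first visit is among the 32. If 0, 8, 16 or 32 of them did so (assumed), then 75, 83, 91 or 107 people contribute to Aim 1. The SAP's power figure (above .80 at d = .40) comes without its inputs, so it is not reproduced here; nothing below depends on it.

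**2. ASI-3 as its own predictor (DT model).** Suppose treatment shifts ASI-3 by .40 SD (the SAP's d, used only as an example).
- Same-visit ASI-3 as predictor: the outcome equals the predictor, so the slope is 1 and the treatment and interaction terms are 0 by identity.
- Other-visit ASI-3, between-visit correlation r (assumed .6 to .8): the treatment term is .40 - r x .40, which is .16 at r = .6 and .08 at r = .8.

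MTPT-C, the other DT outcome, is not subject to this identity.

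**3. ASI-3 as moderator of other targets.** All inputs are assumed. Let baseline ASI have SD 1 and slope b = .5 on the target in controls. Let r be the baseline-to-post correlation of ASI-3 in controls, and let post-treatment ASI-3 have SD 1 there. The slope on post-treatment ASI-3 in controls is then b x r.

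*True moderation of .30 per SD, treatment shifting ASI-3 by a constant:* estimated interaction = .30 x r = .15, .18, .21 for r = .5, .6, .7.

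*No true moderation, r = .6.* Control slope = .5 x .6 = .30.
- Constant shift: treated slope .30, interaction 0.
- Response to treatment varies between people with SD s: treated slope = .30/(1 + s²). At s = .5, .30/1.25 = .24, interaction -.06. At s = .7, .30/1.49 = .20, interaction -.10.
- Treated scores compressed by 20%: treated slope = .30/.80 = .375, interaction +.075.

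*True moderation of .30 with 20% compression, r = .6:* treated slope = .80 x .6/.80 = .60, less .30, gives .30. So attenuation is common but not assured.

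A false interaction therefore needs treatment to change the spread of ASI-3, not only its mean, and it can go in either direction.

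**4. Precision from a baseline value.** Setting: 25 v 25 (equal allocation assumed), one visit, t test, two-sided .05, 80% power. The detectable effect is .809 x sqrt(1 - R²).
- Covariates explaining 10% to 20% (assumed): .809 x sqrt(.90) = .77 and .809 x sqrt(.80) = .72.
- Adding the baseline value: with the covariate composite equally correlated with the baseline and post values (its R² written c), total R² = (c + r² - 2cr)/(1 - c). For c = .10, r = .5 this is .25/.90 = .278, giving .69. For c = .20, r = .7 it is .41/.80 = .5125, giving .56 to .57.

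**5. Loss.** If people with neither visit in one arm differ from those assessed by delta, the all-randomised contrast moves by share x delta. For delta of .3 to .5 SD (assumed), that is .045 to .075 SD at a share of 16/107 = 15.0%, and .09 to .15 SD at 29.9%.

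**The case against.** **Absence of a baseline ASI-3 is inferred.** The baseline list is not said to be exhaustive, and item 2 simply omits the time point. This stands as a caution: the safe statement is that the time point is unspecified and no baseline ASI-3 is described. Against it, the protocol spells out dual timing where it intends it, giving QSU-Brief scores at both baseline and the deprivation window.

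**The analysis is exploratory.** True, and it limits the severity. A reader might infer that the ASI problem contaminates the main Aim 1 contrasts. It does not: those come from models without ASI.

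**A post-only randomised comparison is valid.** Also true. A reader might infer that lacking baseline targets makes Aim 1 biased, or that 30% of those randomised are excluded. The documents support neither. Bias in the contrasts requires loss, or its link to the outcome, to differ by arm; no figure for that is given. The 29.9% includes people who attended the first visit, and a mixed model keeps them. K6+, QSU and BRIEF-A already cover ground close to several targets.

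**The missing-data phrase is a rationale for a method.** It does not define an analysis set, it is correct for one-visit attenders, and no stated figure depends on it. That makes it a wording point only.

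**Dropouts are already to be examined.** Item 4 provides for this. It specifies neither a comparison by arm and visit nor a sensitivity analysis.

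**Conclusion.** The point holds for the ASI moderation. As specified, its interaction has no reading as baseline effect modification for any target, and for the ASI-3 outcome it is uninformative. It may be attenuated (.15 to .21 for a true .30) or spurious in either direction (-.06 to -.10, or about +.08), but these sizes rest wholly on assumed slopes and correlations. It would be wrong to conclude that a false interaction must arise, or that one cannot.

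Baseline PANAS, WSWS and ASI-3 would be an improvement rather than the repair of an error; the gain depends on correlations the documents do not give, and these may be weak for state affect and withdrawal under deprivation. The inclusion wording is a minor overstatement. The size of any bias from loss cannot be derived from the documents.

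Overall severity is minor to moderate: the analysis affected is exploratory, and the SAP's note says the full plan could not be validly carried out.

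**What to change.** 1. **ASI moderator.** If enrolment is open, give ASI-3 at the existing baseline visit, name that value as the moderator in item 2, and omit ASI moderation for the ASI-3 outcome. If no baseline ASI-3 exists, drop the analysis, or report it as a non-causal association for outcomes other than ASI-3.
2. **Baseline covariates (secondary).** If enrolment is open, also give PANAS and WSWS at baseline, and use each of the three baseline values as a covariate for its own outcome. This leaves the working-memory tasks and MTPT-C as they are, and reduces rather than removes bias from loss.
3. **Wording.** Replace the inclusion claim with *all participants with at least one post-treatment assessment*.
4. **Attendance.** Extend item 4 to a table of neither, one or both visits by arm, with a delta-shift sensitivity analysis for those with neither.

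Cost if enrolment is open: three questionnaires and a few minutes at an existing visit, SAP edits, one table and one sensitivity analysis. If it has ended, as the SAP note may suggest, only items 3 and 4 and the no-baseline option in item 1 apply, and no new data are needed.

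### The SAP's fixed covariate list leaves out age, although age is already recorded and no pre-treatment working-memory score is scheduled; adding it to the working-memory models is a cheap, modest improvement

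*SAP*

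**What the plan says.** The SAP (Analytic Plan, opening paragraph) sets one covariate list for all analyses: "cigarette use in the last 30 days, FTCD score, QSU score, BRIEF-A scores for the Behavioral Regulation Index". The fifth and last entry is distress on the K6+. The only demographic variable used anywhere in the analysis is sex, and that is exploratory (SAP, Exploratory Analyses).

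Age is available. Under Baseline Assessments, Demographics, the Protocol states: "Participants will be asked to provide standard demographic information (age, gender, race/ethnicity". Eligibility requires that participants "be between 18 and 65 years of age" (Participant Selection). No stratification by age is described.

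Working memory is measured with "Adaptive N-Back, Digit Span, and Spatial Span" (Protocol, Mechanistic Targets). On timing, the same section says: "Each of the mechanistic targets will be assessed at the post-intervention standard-smoking and deprivation-window assessments". No working-memory task appears under Baseline Assessments.

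Aim 1 compares the randomised arms on these scores. Aims 2 and 3 regress the two lapse outcomes on the measured risk variables, working memory included.

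**The concern.** Adjusting for the pre-treatment value of an outcome is the usual way to remove stable between-person differences. That is not possible for working memory here, because the tasks are first given after the intervention. A recorded baseline variable that predicts task performance would be a partial substitute, and age is a natural candidate in a sample that may run from 18 to 65. The SAP does not use it.

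Two things are at stake, and they differ in kind. In Aim 1, any age-related variation in task scores stays in the error term and widens the intervals for the arm contrasts. In Aims 2 and 3, working-memory level is observed and not assigned. If age relates both to working memory and to lapse behaviour, part of the age relation would be read as a working-memory relation.

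**Working it through.** **Inputs.** Analysed N is 75; the SAP's Power Analysis was run "to calculate the smallest effect size detectable given our N=75 at the deprivation assessment". There are three arms (Protocol, Design Overview: "randomized to one of three intervention conditions"). The allocation ratio is not stated, so 1:1:1, or 25 per arm, is assumed. Alpha is not stated, so two-sided 5% is assumed. The Aim 1 effect is d = .40 (SAP, Power Analysis). The documents give no correlation between age and working memory, or between age and lapse, so ranges are used.

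**Step 1: the SAP's own figure.** The SAP states power above .80 at d = .40. For a 25 v 25 contrast, the noncentrality is .40/√(2/25) = 1.414. Power is .29, both by the normal approximation (.293) and by the noncentral t with 75 − 3 − 5 = 67 df (.286). The d detectable with .80 power is about .80. The stated figure is therefore not reproduced for a between-arm contrast, but the variance inputs to the SAP's power program are not reported. This is a separate matter. It is used here only to fix the starting point.

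**Step 2: precision in Aim 1.** Let r be the correlation of age with the working-memory score given the five covariates. Residual variance is multiplied by (1 − r²), the SE by √(1 − r²), and effective N is 75/(1 − r²). With age added, df = 66 and the noncentrality is 1.414/√(1 − r²). For r = .3: 75/.91 = 82.4, and 1.414/.954 = 1.482.

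| Assumed r | SE ratio | Effective N | Noncentrality | Power at d = .40 | Detectable d |
|---|---|---|---|---|---|
| age omitted | 1 | 75 | 1.414 | .29 | .80 |
| .1 | .995 | 76 | 1.421 | .29 | .80 |
| .2 | .980 | 78 | 1.443 | .30 | .79 |
| .3 | .954 | 82 | 1.482 | .31 | .77 |
| .4 | .917 | 89 | 1.543 | .33 | .74 |
| .5 | .866 | 100 | 1.633 | .36 | .70 |

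One extra coefficient costs about √(67/66) − 1 = 0.8% of the SE. At r = .1 this cancels the gain (.995 × 1.0076 = 1.002).

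**Step 3: confounding in Aims 2 and 3.** Suppose working memory has no relation to lapse of its own. The spurious correlation is then ρ = r(age, working memory) × r(age, lapse). For a test of one correlation with five covariates, df = 75 − 2 − 5 = 68 and the noncentrality is √68 × ρ/√(1 − ρ²).

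| Assumed pair | ρ | Noncentrality | Rejection rate (nominal 5%) |
|---|---|---|---|
| .2 × .1 | .02 | 0.165 | 5% |
| .3 × .1 | .03 | 0.247 | 6% |
| .3 × .2 | .06 | 0.496 | 8% |
| .4 × .2 | .08 | 0.662 | 10% |
| .5 × .2 | .10 | 0.829 | 13% |

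A simulation without covariates (N = 75, 20,000 runs per cell) gave 5.5%, 6.0%, 8.2%, 10.1% and 14.0% for the same pairs. Both are simplifications: the planned Aim 2 model enters the scores from both contexts together and has two outcomes.

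**The case against.** The strongest reply is that the premise is not in the documents. Nothing in them says that age predicts these tasks in this population. The 47-year span is an eligibility window and not the spread of the sample. The list already contains an executive-function measure (the BRIEF-A index), and the Protocol describes working memory as central to executive functions. If span scores are age-normed, which is not stated, little age variation would remain in those tasks. All of this stands. It is why r is taken as conditional on the other covariates, and why the range starts at .1, where the gain is nil.

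A reader might infer that a chance age imbalance biases the Aim 1 contrasts. It does not. Chance imbalance is already part of the unadjusted standard error, and the test is valid under randomisation. Counting it beside the variance loss would count one cost twice. Attrition (75 assessed of up to 107 randomised) could disturb balance, but nothing in the documents ties it to age.

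A reader might also infer that the Aim 2 and 3 slopes are confounded by age. The documents support only that they could be. Aim 2 is framed as association. No relation between age and lapse is documented, and 30-day cigarette use and FTCD score may already absorb one.

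Finally, the SAP's opening note says the sample was too small for the whole plan to be carried out validly. This limits the practical weight of the point. It does not remove it for any working-memory analysis that is reported.

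**Conclusion.** The point holds as an inexpensive improvement to the working-memory models, with moderate confidence. The documentary facts are clear: age is recorded but unused, and no baseline working-memory score exists to take its place.

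The size is assumption-dependent. In Aim 1 the SE falls by roughly 5% to 13% before the 0.8% cost if r is .3 to .5, by about 2% at .2, and not at all in net terms at .1. Power at d = .40 stays at or below .36 throughout, so age does not repair the power shortfall. In Aims 2 and 3 the excess of false positives runs from negligible to about 8 percentage points over the assumed range, and only if age relates to lapse given the smoking covariates. All figures rest on 25 per arm, two-sided 5% and N = 75, which the SAP's own note suggests is optimistic.

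The documents do not support extending the argument to the stress and distress-tolerance models of Aim 1. The missing baseline working-memory score is the larger gap, and age is only a partial proxy for it.

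**What to change.** Add age at baseline to the covariates of the Aim 1 working-memory model and of the Aim 2 and 3 models that contain working-memory predictors. State in the SAP whether the span scores are raw or age-normed, since this decides how much age can contribute.

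No new data are needed. The statistical cost is one coefficient per outcome: three in the working-memory MANCOVA if the age slope is allowed to differ by task. The burden is most noticeable in Aim 3, which may already carry up to 14 risk terms (7 assays × 2 contexts) and five covariates at N = 75. If the main analyses have already been run, report the age-adjusted working-memory results beside them, labelled as a sensitivity analysis.
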